#### From the Physical Well-being questions:

- 1: I have a lack of energy
- 2: I have nausea
- 5: I am bothered by side effects of treatment
- 7: I am forced to spend time in bed

#### And from the Functional Well-being questions:

1: I am able to work

Change from baseline will be categorized as: Improved, Stable, Worsening 1 category, Worsening 2 categories, Worsening 3 categories, or Worsening 4 categories. This will be summarized in a table and may be displayed graphically.

#### 10.3.4 Patient-reported Outcome of EQ-5D-5L

Analyses of changes from baseline will be analyzed for each scheduled post-baseline visit and for the final visit for the EQ-5D-5L instrument and the EQ VAS. Patients who do not have both a baseline measurement and at least 1 post-baseline measurement will not be included.

The final visit is defined as the last assessment within 28 days after date of last dose of oral study drug for those that discontinued oral treatment or prior to the visit cut-off date for those still ongoing. For the protocol-specified post-baseline visits; the EQ-5D-5L assessment will be grouped in actual scheduled visit windows as described in Table 3. If more than one assessment date falls within a given visit window, the one that is closest to the actual scheduled EDC visit date will be used. In the case of ties, the assessment prior to the scheduled visit date will be used. The data sets will highlight the value for the patient that was included in the summary table, wherever feasible. The summary tables and graphs will only display data if the number of observations is greater than 10 in each treatment arm.

At a given visit, the change from baseline will be analyzed for the treatment comparisons using an Analysis of Covariance (ANCOVA) with treatment and stratification variables as categorical factors and baseline measurement for the parameter as a continuous covariate. In addition, a graphical presentation of mean changes over time may be presented.

#### 10.3.5 PRO Patient Disposition and Completion Rate

The following analyses will also be summarized in order to characterize PRO data (eg, FACT-O and EQ-5D-5L) completeness.

PRO patient disposition will be summarized in a table with the cumulative patient disposition by treatment and PRO assessment window for each scheduled post-baseline visit (eg, Cycle 1 Day 1, Cycle 2 Day 1, etc.) . The following categories will be summarized:

- PRO assessment expected;
- PRO assessment not expected due to disease progression;
- PRO assessment not expected due to other reasons; and
- Patient ongoing in study, PRO assessment not yet reached.

Overall PRO completion rates, as well as the breakdown of electronic versus paper version, will be summarized for each PRO assessment window. Overall completion rate is defined as the number of patients having at least 1 response in the PRO instrument, divided by the number of patients expected to have completed a PRO assessment at a given visit.

#### 10.3.6 PRO Correlation With Adverse Events

The correlation between EQ-5D-5L and FACT-O will be summarized by tabulating the mean EQ-5D-5L subscale score for the mobility, self-care, and usual activities dimension at each cycle broken down by response to FACT-O item GP1 (I have lack of energy) as well as by grade 1, 2, or 3 CTCAE maximum grade of asthenia/fatigue. The mean EQ-5D-5L subscale score of self-care and usual activities at each cycle will be broken down by response to FACT-O item GP2 (I have nausea) as well as by grade 1, 2, or 3 CTCAE maximum grade of nausea.

#### 10.3.7 Evaluation of Post-progression Efficacy Endpoints

Following treatment discontinuation, subsequent anticancer treatments will be collected for all patients every 12 or 24 weeks ( $\pm$  14 days), until death, loss to follow-up, withdrawal of consent from study, or closure of the study. The subsequent anticancer data with start and stop date and any date of progression documented for each regimen will be recorded. The following endpoints will be derived based on these data.

- Chemotherapy-free interval (CFI), will be calculated in months as the time since the last dose of the most recent chemotherapy regimen to the date of the first dose of a subsequent chemotherapy, or death due to any cause, + 1 day. Patients without a documented start of a subsequent chemotherapy after study drug will be censored on the date the patient was last known to be alive or last visit.
- Time to first subsequent anticancer treatment (TFST), will be calculated in months as the time from randomization to the date of the first dose of the first subsequent anticancer treatment regimen, or death due to any cause, + 1 day. Patients without a documented start date of a subsequent anticancer treatment will be censored on the date the patient was last known to be alive or last visit.
- Time to second subsequent anticancer treatment (TSST), will be calculated in months as the time from randomization to the date of the first dose of the second subsequent anticancer treatment regimen, or death due to any cause + 1 day. Patients without a documented start of a second subsequent anticancer treatment will be censored on the date the patient was last known to be alive or last visit.
- Time to treatment discontinuation of oral dose (TDT), will be calculated in months as the time from randomization to the date of the last dose of oral treatment + 1 day. Patients still ongoing will be censored at the last visit prior to the visit cutoff.

The same statistical test used for the primary endpoint (ie, stratified log rank test and a stratified Cox proportional model) will be used to compare treatments for this endpoint.

#### 10.3.8 Pharmacokinetic Analysis of rucaparib

As an exploratory endpoint, trough  $(C_{min})$  concentrations of rucaparib will be summarized with descriptive statistics by cycle in all patients with at least 1 PK sample collected.

### 10.4 Examination of Efficacy in Subgroups

The primary endpoint (invPFS) will be further explored within the ITT Population for the following subgroups:

- The stratification factor used for randomization.
  - HRD classification (tBRCA, non-tBRCA LOHhigh, non-tBRCA LOHlow, and non-tBRCA LOHunknown);
  - Disease status post chemotherapy (no residual disease vs residual disease); and
  - Timing of surgery (primary surgery vs. interval debulking).
- Age groups ( $< 65, 65-74, \ge 75$ );
- Race (White, Other, Unknown);
- Geographic region (United States/Canada, Europe, Eastern Europe, Latin America, Asia, Australia/New Zealand).
- ECOG  $(0, \ge 1)$
- FIGO Stage at Diagnosis (III or IV)
- CA-125 at Baseline (≤ ULN or > ULN) using central laboratory
- Prior use of bevacizumab (Yes or No); and
- Surgery outcome (R0 vs other).
- Disease status at baseline;
  - Measurable disease by investigator (ie, target lesions identified by RECIST v1.1);
  - non-measurable disease by investigator (ie, non-target lesions only identified by RECIST v1.1);
  - No disease by investigator (ie, no target lesions and no non-target lesions identified by RECIST v1.1);
- Disease Free with normal CA-125 defined as Best radiological response (CR, No Disease Post-surgery) and CA-125 ≤ ULN (Yes, No)

In addition, primary endpoint of invPFS will be analyzed for the following tBRCA mutation subgroups:

- Mutation: BRCA1 vs BRCA2; and
- Mutation type: Germline, Somatic, or Unknown.

Clovis Oncology 10 February 2022

These exploratory subgroup analyses of invPFS will be analyzed using Cox proportional hazards methodology. The hazard ratio from the Cox proportional hazards model will be used to estimate the HR with 95% CIs between the randomized treatment groups. In addition, an interaction test of the subgroup-by-treatment interaction term in the Cox proportional hazards model. All these analyses will be performed using a unstratified model due to smaller sample sizes.

In addition, a log-rank test of invPFS between the randomized treatment groups together with a graphical presentation of invPFS distributions, median invPFS with 95% CI, and event rates will be presented as supportive statistics for these subgroups. Furthermore, the probability of being progression free at 6, 12, 18, and 24 months may be summarized for some of the subgroups by treatment group by using the Kaplan-Meier estimates, at each time point with 95% CIs using a log-log distribution.

#### 11 SAFETY ANALYSIS

Only patients who are randomized to Arm B (rucaparib monotherapy) and Arm D (placebo) are included in the Safety Population for ATHENA-MONO. The safety analyses will be presented for the Safety Population presenting the data by each treatment group separately.

Summary tables are based on data that are found to be "on-treatment"/ "treatment-emergent" for the oral study drug as outlined in the below sections. This is regardless of whether these data were "on-treatment"/ "treatment-emergent" for IV study drug.

#### 11.1 Adverse Events

AEs will be classified using the MedDRA version 24.1 or higher classification system. The severity of the toxicities will be graded according to the NCI-CTCAE v5.0 or later.

All safety data which are considered treatment-emergent to oral study drug will be summarized. Treatment-emergent to oral study drug: is defined as safety data with an onset date on or after the date of first dose of oral study medication until the date of the last oral study medication plus 28 days. AEs will be considered treatment-emergent to oral study drug if all or part of the date of onset of the AE is missing and it cannot be determined if the AE meets the definition for treatment-emergent.

The number and percentage of patients who experience TEAEs to oral study drug will be presented by SOC and PT. Multiple instances of the AEs in each SOC and multiple occurrences of the same PT are counted only once per patient. The number and percentage of patients with at least 1 TEAE to oral study drug will also be summarized.

The incidence of TEAEs will be summarized by relationship to either oral or IV study drug according to the following categories: "treatment-related," or "not treatment-related". If a patient experiences multiple occurrences of the same AE with different relationship categories, the patient will be counted once, as a relationship category of treatment-related.

A summary table with the number and percent of patients that fall into each of the AE categories below will be presented for all events, related to oral study drug, and related to IV study drug. In addition, separate tables by SOC and PT will be presented for each of these AE categories:

- All TEAEs;
- Serious TEAEs:
- Grade 3 or greater TEAEs;
- TEAEs that led to death;
- TEAEs that led to oral study drug discontinuation;
- TEAEs that led to IV study drug discontinuation;
- TEAEs that led to discontinuation of both oral and IV treatment;

- TEAEs that led to dose reduction of oral study drug;
- TEAEs that led to oral study drug interruption;
- TEAEs that led to IV study drug interruption;
- TEAEs that led to both oral and IV study drug interruption;
- TEAEs that led to dose reduction or interruption of oral study drug.
- TEAEs that led to dose reduction, interruption, or discontinuation of oral study drug

If a patient experiences multiple occurrences of the same AE with different toxicity grades, the patient will be counted once for the maximum (most severe) toxicity grade. AEs with a missing toxicity grade will be presented in the summary table with a toxicity grade of "Missing." For each toxicity grade, the number and percentage of patients with at least 1 TEAE of the given maximum grade will be summarized.

The time to the first TEAE of Anaemia or Haemoglobin decreased, and first TEAE leading to a dose reduction, interruption, and/or discontinuation of oral study drug is defined as 1+ the number of days from the first dose of study drug to the start of the first AE. The cumulative incidence is presented in a 1-KM graph for only the patients with an event and the median time to onset will be calculated together with the 95% CI.

Non-TEAEs (pre-treatment and post-treatment) will be presented in the by-patient data listings for the Safety Population.

MedDRA PTs will be combined for the following similar terms:

- Anaemia or Haemoglobin decreased;
- Asthenia or Fatigue;
- ALT or AST increased;
- Neutropenia or Neutrophil Count decreased;
- Thrombocytopenia or Platelet count decreased.

In addition to the cumulative incidence tables of AEs, time adjusted AE summaries for the oral treatment study duration will be created. The time adjusted analyses (ie, 100 patient-treated years) of AEs are defined as the number of total events of a certain AE divided by the patient-years. The patient-years is the total sum of all the years the patients in each treatment arm are treated (ie, from the start of first oral dose to date of last oral dose +1 day). The time adjusted analyses will be summarized for the following:

- 100 patient-treated years for all TEAEs;
- 100 patient-treated years for Grade 3 or greater TEAEs; and
- 100 patient-treated years for serious TEAEs.

In addition, the analysis of combined terms for anemia is explored as a time to first event analysis as described above. Transfusions (blood or plasma) and concomitant medications / growth factor support are provided in patient listings. The number of transfusions is also summarized.

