- Disease status (no residual disease vs residual disease); and
- Timing of surgery (primary surgery vs interval debulking).

Randomization to study treatment must occur within 8 weeks following a patient's first day of the last cycle of chemotherapy.

During the Double-blind Treatment Phase (continuous 28-day treatment cycles), the double blinded oral study treatment will be administered on Day 1 of Cycle 1 and continue BID throughout the cycle as monotherapy. IV study drug administration will begin on Day 1 of Cycle 2 during the Double-blind Treatment Phase. Patients will have clinic visits on Day 1 and Day 15 of Cycles 1 and 2, and on Day 1 of every cycle thereafter. Study treatments will continue until 24 months after planned initiation of oral/ IV combination study treatment

(C2D1), disease progression, unacceptable toxicity, or withdrawal of participant consent, whichever happens first.

During the Treatment Phase patients will be monitored for safety and efficacy. Assessments will include AEs, physical examination, vital signs and weight measurement, central laboratory hematology, serum chemistry, and CA-125 measurement, concomitant medications, therapies, and procedures, ECOG performance status, disease status assessment, ctDNA analysis, study drug administration and accountability, and PRO. ECGs and urinalysis will be performed as clinically indicated. Blood samples will also be collected to determine whether any mutation identified is of germline or somatic origin.

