Due to the approval of olaparib for BRCA-mutated patients in the first-line maintenance setting (SOLO1 study), the enrollment of tBRCA is lower than originally anticipated in the sample size assumptions in the original protocol. Thus, the monotherapy treatment comparison, comparing Arm B (oral rucaparib + IV placebo) versus Arm D (placebo [oral and IV]), will start with the HRD Population, then ITT Population for the step-down hierarchical testing and the tBRCA subgroup will be explored as an exploratory endpoint.

The Phase 3 PRIMA study of niraparib also provided information regarding treatment effects in a similar population for those patients who are HRD and for the ITT Population. Due to the above changes to the alpha level and step-down, the adjusted power assumption for the monotherapy treatment comparison, comparing Arm B (oral rucaparib + IV placebo) versus Arm D (placebo [oral and IV]), is summarized in the table below.

T 1 1777) 1 4 4 17 17 4 4 4	Monotherapy Treatment C	omparison: Arm l	B (oral rucapa	arib + IV placebo)	vs Arm I	) (placebo
[oral and IV]), randomization allocation 4:1	[oral and IV]), randomizati	on allocation 4:1				

oral and 1 v j), randomization anotation 4.1						
Protocol Version	Group	Cumulative N (4:1)	Number of Events	HR Median PFS	Power	One-sided Alpha
	tBRCA	170 (135:34)	120	HR 0.50, 18 vs 36 months	90%	0.008
Original Protocol and Amendment 1	HRD	340 (270:68)	230	HR 0.60, 15 vs 25 months	90%	0.008
	ITT	500 (400:100)	340	HR 0.65 12 vs 17 months	90%	0.008
Amendment 2	HRD	205 (164:41)	123	HR 0.45  12 vs 26.7 months	90%	0.0125
	ITT	500 (400:100)	300	HR 0.60  12 vs 20 months	90%	0.0125

Abbreviations: HR = hazard ratio; HRD = homologous recombination deficient (tBRCA + non-tBRCA LOHhigh); ITT = intent-to-treat, IV = intravenous; PFS = progression-free survival.

The power assumption for the combination treatment comparison is still set at 90% power for both HRD Population and ITT Population as per the original protocol, as shown in the table below.

The following table provides the sample size and power for the clinically relevant comparison between Arm A (oral rucaparib + IV nivolumab) and Arm B (oral rucaparib + IV placebo) within the HRD Population and ITT Populations.

Combination Treatment Comparison: Arm A (oral rucaparib + IV nivolumab) vs Arm B (oral rucaparib + IV placebo), randomization allocation 4:4							

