#### 7 STUDY DRUG EXPOSURE AND COMPLIANCE

Oral study drug exposure will be summarized for all patients in the Safety Population. The duration of oral study drug exposure will be calculated as the number of days from the first dose of study drug to the day of the last dose of study drug +1. For patients that are ongoing at the time of the visit cut-off, the date of the visit cut-off will be used as the end date for oral treatment. The duration will be summarized with summary statistics and by categories  $(0-6 \text{ months}, \ge 6 \text{ to } 12 \text{ months}, \ge 12 - 24 \text{ months}, \ge 24 \text{ months})$  for each treatment arm. The oral dose intensity will be summarized and is defined as time normalized actual dose received divided by the starting dose of 600 mg BID.

For oral study drug, the number of patients with at least 1 dose reduction due to a TEAE based on the dosing log will be summarized with frequencies and percentages. Any dose reduction regardless of duration will be summarized. In addition, protocol-specified dose reductions will be broken up by dose level and by reason (ie, AE, non-compliance, or other). That is, the number of patients on each protocol-specified oral dose level will be summarized (ie, 600 mg BID, 500 mg BID, 400 mg BID, 300 mg BID, etc.) in order to assess patients with multiple levels of oral dose reductions. Dose reduction is defined as 3 or more consecutive days at that protocol-specified dose level. The number of patients with at least 1 dose re-escalation will be summarized for each protocol-specified oral dose level from which they escalated.

The number of IV cycles given per treatment arm will also be summarized.

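### MONO SAP 11.1 counts adverse events to 28 days after the last oral dose but person-time only to the last dose, overstating each arm's rate by roughly 5 to 7% at planned exposures

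*SAP*

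**What the plan says.** MONO SAP 11.1 defines an event as treatment-emergent to oral drug if its onset falls between the first oral dose and a closing date described as "until the date of the last oral study medication plus 28 days". The same section plans time-adjusted rates, which "are defined as the number of total events of a certain AE divided by the patient-years". Total events are counted, not patients with an event. Three tables are listed: "100 patient-treated years for all TEAEs", and the same for Grade 3 or greater and for serious treatment-emergent events (TEAEs). Patient-years are the summed treated time in each arm, "ie, from the start of first oral dose to date of last oral dose +1 day". The added day only makes the day count inclusive.

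MONO SAP 7 covers patients still on drug at the analysis: "the date of the visit cut-off will be used as the end date for oral treatment". No section restricts these tables to events on dose, and none adds the 28 days to the patient-years. The COMBO SAP lists no such rates, so the point is confined to the monotherapy comparison.

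**The concern.** A rate per person-time needs events and time taken from the same window. Here every patient who has stopped can contribute up to 28 days of events and no time for those days. The window is not empty by design: Protocol 8.7 records all adverse events through 28 days after the last dose of oral or IV drug, whichever is later.

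The tables exist to make arms with different treatment durations comparable. The excess is itself larger where treatment is shorter, so some of the dependence on duration that the adjustment should remove stays in. At stake are the absolute rates per arm and, to a smaller degree, the comparison between arms.

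**Working it through.** The documents give no exposure-adjusted rate and no mean exposure, so there is no planned figure to reproduce. The exposures in steps 2 to 4 are illustrations.

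**Inputs**
- Event window: last oral dose + 28 days (MONO SAP 11.1).
- Person-time: to last oral dose + 1 day (MONO SAP 11.1).
- W = 28/30.4375 = 0.920 months.
- Planned ITT median PFS, placebo vs rucaparib: "12 vs 20 months" (MONO SAP 2.3.2, Amendment 2 row). These medians agree with the stated hazard ratio, 12/20 = 0.60.
- Treatment cap: "Study treatments will continue until 24 months after planned initiation of oral/ IV combination study treatment" (MONO SAP 2.2). With one oral-only cycle first, this is 24 + 0.92 = 24.92 months of oral drug.

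**1. Excess within an arm.** Let T be mean exposure and k the post-dose event rate divided by the on-dose rate. If all patients have stopped, planned rate / on-dose rate = 1 + kW/T. With k = 1 the excess is W/T:
- 6 months: 0.920/6 = 15.3%
- 12 months: 0.920/12 = 7.7%
- 18 months: 0.920/18 = 5.1%

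**2. Illustrative exposure.** Assume exponential time to progression, treatment stopping at progression, and the cap. Then T = (1 − exp(−λ × 24.92))/λ, with λ = ln 2/median.
- Rucaparib (median 20): T = 16.69 months, excess 0.920/16.69 = 5.5%.
- Placebo (median 12): T = 13.21 months, excess 0.920/13.21 = 7.0%.
- Rate ratio, rucaparib to placebo: multiplied by 1.0551/1.0696 = 0.986.

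**3. Other assumptions (rucaparib, placebo, factor on the rate ratio)**
- Planned HRD medians, 26.7 vs 12 months: 5.0%, 7.0%, 0.982.
- 25% of rucaparib and 10% of placebo patients still on drug at cut-off (assumed): 4.1%, 6.3%, 0.980.
- Rucaparib k = 0.5, placebo k = 1 (assumed): 2.8%, 7.0%, 0.961.
- Rucaparib k = 1, placebo k = 0.5 (assumed): 5.5%, 3.5%, 1.020.

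The last two rows are measured against the on-dose rate. Measured against the rate with the 28 days added to person-time, the factor is 1 + W/T whatever k is, because the events are the same and only the denominator changes.

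**4. Difference scale.** With k = 1 the error in the rate difference is W × (rB/TB − rD/TD), where rB and rD are the true rucaparib and placebo rates. It favours rucaparib only if rB/rD is below TB/TD = 16.69/13.21 = 1.26.
- True rates of 100 and 100 per 100 patient-years are reported as 105.5 and 107.0, a difference of −1.5 instead of 0.
- Assumed true rates of 200 and 100 are reported as 200 × 1.0551 = 211.02 and 100 × 1.0696 = 106.96, a difference of 104.06 instead of 100, which makes rucaparib look worse.

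**5. After alignment.** With 400 and 100 patients, adding the 28 days raises patient-years from 556.3 to 587.0 for rucaparib and from 110.1 to 117.7 for placebo. True rates of 100 and 100 are then reported as 100 and 100.

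**The case against.** The best defence is that the denominator is openly time on treatment. The tables are labelled by patient-treated years, and the SAP says that "time adjusted AE summaries for the oral treatment study duration will be created". That could mean that only events on dose are to be counted. But the listed outputs are TEAEs, a defined term that includes the 28 days. MONO SAP 11 treats on-treatment and treatment-emergent as one basis for its summary tables, and 11.2 and 11.3 run the on-treatment period for laboratory values and vital signs to the same 28 days. If on-dose events are meant, the text has to say so, and either reading needs an edit.

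Three further objections stand and limit the point. Patients still on drug at cut-off add no post-dose window, and MONO SAP 2.3.2 allowed a read-out as early as 15 months after the last randomization, so there may be some. The tables are descriptive, come on top of the cumulative incidence tables, and feed no test. The MONO primary analysis has already been run.

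A reader might also infer that the rule makes rucaparib look safer, because the planned medians suggest shorter exposure on placebo. The documents do not support that as a conclusion. They give no observed exposure and no placebo event rates. Against the on-dose rate, the ratio moves that way only if post-dose and on-dose rates relate similarly in both arms. On the difference scale, the sign depends on the true rates.

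**Conclusion.** The mismatch is explicit and nothing in the documents reconciles it. Followed as written, the rule overstates each arm's rate whenever events occur in the 28 days. The size is about 28 days divided by mean exposure, on the assumptions that all patients have stopped and events continue at the on-dose rate; it is less if some are still on drug or events fall off after stopping. At exposures implied by the planned ITT medians and the cap, that is about 5.5% for rucaparib and 7.0% for placebo. The effect on the rate ratio is small: a factor of about 0.986, with about 0.96 to 1.02 across the scenarios tried. The direction of the error in the between-arm contrast, above all in the rate difference, cannot be fixed from the documents. This is a minor point about descriptive safety summaries; no tested endpoint is touched.

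**What to change.** Use the same window for events and person-time in all three rate tables, in one of two ways:

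- End each patient's person-time at the earliest of last oral dose + 28 days, death, visit cut-off, or end of adverse-event collection, and count only events with onset inside that time. End of collection includes withdrawal and loss to follow-up. For serious TEAEs it also includes the start of subsequent anticancer therapy, because Protocol 3.1.6 and 7.5.4.1 stop SAE collection at that point except for MDS and AML. Without this last limit, the serious-event rate would be diluted by time in which most such events are not collected.
- Or keep the present patient-years and count only events with onset up to the last oral dose.

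The two give the same rate only if the post-dose rate equals the on-dose rate, so the table should state which was used.

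The cost is one phrase of definition and a re-run of three tables, with no new data. The COMBO SAP (2.3 and 3.5) dates the MONO primary analysis to 23 March 2022, so this can no longer be a prospective edit. It should appear as a corrected or supplementary table with a footnote, for example with any safety update that accompanies the final OS analysis still planned in MONO SAP 10.2.2.
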